6 STUDY INTERVENTION(S) OR EXPERIMENTAL MANIPULATION(S)

6.1 STUDY INTERVENTION(S) OR EXPERIMENTAL MANIPULATION(S) ADMINISTRATION

6.1.1 STUDY INTERVENTION OR EXPERIMENTAL MANIPULATION DESCRIPTION

The Vielight Neuro Gamma device, manufactured by Vielight, Inc. (Toronto, Canada) will be used in the study. The parameters of the non-invasive, non-thermal, non-laser PBM device are summarized in Table 1. Although the Vielight Neuro Gamma device is not presently labeled for treating dementia or AD, it is considered a non-regulated, “low risk general wellness product” according to the Food and Drug Administration.

Table 1. Parameters of the Vielight Neuro Gamma Device

Source	light emitting diode (LED)
Wavelength, nm	810
Power output, mW	100 (posterior transcranial LEDs); 75 (anterior transcranial LED); 25 (intranasal LED)
Power density per LED, mW/cm²	100 (posterior transcranial LEDs); 75 (anterior transcranial LED); 25 (intranasal LED)
Pulse frequency, Hz	40
Pulse duty cycle, percentage	50
Duration of each treatment session, minutes	20
Frequency of treatment	3x/week
Beam spot size, cm²	≈1
Energy delivered, Joules	225 (transcranial headset); 15 (intranasal LED)
Energy density per LED, J/cm²	225 (transcranial headset); 15 (intranasal LED)
Dose of each treatment session, Joules	240
Cumulative energy density per LED, per week	675 (transcranial headset); 45 (intranasal LED)
Cumulative dose per week, Joules	720

6.1.2 ADMINISTRATION AND/OR DOSING

The Vielight Neuro Gamma device has light emitting diodes mounted on a headset that targets key nodes of the default mode network (DMN), including one frontal array, two parietal arrays, one posterior array that targets the precuneus and posterior cingulate cortex, and one intranasal probe that targets the mesial temporal lobe. The device delivers infra-red light transcranially at $\lambda = 810$, nm, 40 Hz, 40-150 mW/cm². These dosimetry parameters achieve 0.9 - 11% transmittance through soft tissue and human skull (Salehpour et al., 2018). tPBM will be administered every other day (or at least 3 times a week) in 20-min fractions for 16 weeks. Patients and study companions will be instructed on the use of the device at rest

(e.g., before going to bed), every other day or 3 times a week (e.g., Monday, Wednesday, and Friday). The sham group will be given the same instructions for use and used the same device, except that the device was blindly set to power output of 0 mW/cm². Because the device uses light emitting diodes, it does not produce heat or noise, and the 810 nm wavelength produces non-visible energy. These features were relied on to maintained participants blinded to group allocation.

6.2 FIDELITY

6.2.1 INTERVENTIONIST TRAINING AND TRACKING

Study partners will be trained how to position the Vielight Neuro device on the patient, how to administer the tPBM treatments, how to control, clean and maintain Vielight Neuro device in a single session. One week after the training session, the study partners will be asked to demonstrate their ability to correctly position the device and to administer tPBM treatments to the patients. Any mistakes will be corrected, and study partners will be re-trained if necessary. The study partners will be asked to log the tPBM treatments throughout the 16-weeks in a home treatment diary. A study staff will contact the patient and study partner twice a month to assess for adverse events.

6.3 MEASURES TO MINIMIZE BIAS: RANDOMIZATION AND BLINDING

Subjects will be randomized 1:1 to either tPBM or sham. Study co-investigator ([name]) will provide the randomization list to study staff as eligible participants are enrolled. Blinding will be maintained because the Vielight Neuro Gamma devices use light emitting diodes, and it does not produce heat or noise, and the 810 nm wavelength produces non-visible energy.

[name] will give study staff sealed envelopes with the codes for participant randomizations. The envelopes would be opened only in a situation where an SAE is determined as possibly or potentially related to study intervention. The breaking of the blind will be reported to the IRB, as part of the SAE report.

7 STUDY INTERVENTION/EXPERIMENTAL MANIPULATION DISCONTINUATION AND PARTICIPANT DISCONTINUATION/WITHDRAWAL

Subjects may be withdrawn from the study for any of the following reasons:

1. Subject's or Caregiver's choice to withdraw their consent to participate. Any participant has the right to withdraw from the study at any time and for any reasons without prejudice to future medical care by the physician or the institution. This will be considered a screening failure if they withdraw from the study prior to being randomized. Participants who withdraw consent after randomization will have any available data evaluated, up to the time of withdrawal.
2. Investigator's choice to withdraw the subject from the study. This will be considered a screening failure if the Investigator withdraws the patient prior to randomization.
3. Study termination for either administrative or safety reasons.

For participants who are noncompliant with follow up visits, every effort will be made to collect the data requested by this protocol through the follow up period. All data collected up until the period the subject has withdrawn from the study will be used for this study.

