3 OBJECTIVES AND ENDPOINTS

The primary objective of the study is to assess the safety and tolerability of home transcranial photobiomodulation (tPBM) treatments delivered with a commercially available PBM device (i.e., the Vielight Neuro Gamma device). The primary endpoint will be all adverse events.

The secondary objects of the study are to examine the effects of home tPBM on cognition, behavior, and fluid biomarkers of AD in patients with biomarker confirmed diagnoses of mild-to-moderate AD. Secondary endpoints will be change in the Alzheimer's Disease Assessment Scale, Cognitive Subscale (ADAS-cog), and change in fluid biomarkers of AD (e.g., A β 40, A β 42, total and phosphorylated tau, neurofilament light chain).

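### Does handing the randomization list to study staff unblind the people who collect adverse events, the primary endpoint?

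*Combined protocol and SAP*

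**What the plan says.** On allocation, section 6.3 has a co-investigator who "will provide the randomization list to study staff as eligible participants are enrolled". The next sentence gives the basis for blinding: "Blinding will be maintained because the Vielight Neuro Gamma devices use light emitting diodes, and it does not produce heat or noise", together with the light being invisible. The same section adds that the co-investigator "will give study staff sealed envelopes with the codes for participant randomizations" and sets a rule for their use: "The envelopes would be opened only in a situation where an SAE is determined as possibly or potentially related to study intervention". It closes with a reporting duty: "The breaking of the blind will be reported to the IRB".

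Section 6.1.2 says that in the sham group "the device was blindly set to power output" of zero, that this group has the same device and instructions, and that participants are kept blind by the device's features.

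On the endpoint, section 3 states: "The primary endpoint will be all adverse events". Section 6.2.1 states: "A study staff will contact the patient and study partner twice a month to assess for adverse events". Section 8.2 repeats the calls, and section 8.3.4 has the investigator ask about events at visits and check-ins. Section 8.3.3.2 leaves relatedness to the investigator, and section 10.1.4 has a named team member (name removed) classify each event. Section 9.3.2 compares the number of events between arms. Section 8.1 says that the cognitive and behavioural measures are rated by a staff member who is blind.

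**The concern.** Read alone, the list sentence gives allocation information to the group from which the adverse event callers are drawn. A lack of heat, noise or visible light can blind the person wearing the device, but it cannot blind someone who has read the arm on a list. The authors wrote assessor blinding into section 8.1 for secondary measures and wrote nothing similar for adverse events.

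If callers did know the arm, they might probe harder in one group. That would alter the number of events recorded and so bias the comparison in section 9.3.2. Staff may also take consent (section 10.1.1.2), so a list of arms released in advance could show enrolling staff what comes next.

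**Working it through.** No formula applies, and the plan gives no figure to reproduce. The check is whether each reading of the list sentence fits the other statements.

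**Reading A: the list shows tPBM or sham.**
- Sealed envelopes (6.3): redundant, because the staff who hold them already know what is inside.
- Restriction on opening (6.3): restricts nothing.
- IRB report when the blind is broken (6.3): there is no staff blind left to break.
- Blind rater (8.1): this person is one of the study staff, so the list could not have gone to all of them.
- Blind setting of the sham device (6.1.2): hard to square with staff working from named arms.

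**Reading B: the list carries codes, and the key is sealed.**
- Envelopes, opening rule and IRB report: each has a clear function.
- Blind rater and blind device setting: both possible as written.
- Device properties: they cover the participant, while the coding covers staff.

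Reading B fits every statement. Reading A leaves the three envelope provisions without purpose for the staff who hold the list, and it strains the other two.

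**Following the adverse event data under reading B.**
1. Participants, who report events, are stated to be blind (6.1.2).
2. Callers and the investigator ask in both arms on the same schedule (6.2.1, 8.2, 8.3.4). They learn an arm only if an envelope is opened.
3. Section 8.3.4 requires every event to be documented whatever its relation to treatment. That limits discretion over what is counted, though not over how hard someone probes.
4. Classification by severity or relatedness does not change an all-event count. The exception is an abnormal diagnostic result, which section 8.3.1 can make an adverse event on the investigator's view of its clinical significance. That could bias the comparison only if the investigator knew the arm.

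**Foreseeing assignments.** Section 6.3 ties provision of the list to enrolment of eligible participants, which fits stepwise release. Under that release, or with codes alone, enrolling staff cannot see the next arm. No passage says that future assignments are visible.

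**Size.** Bias from this source is nil if the list is coded. If it were not, the documents give no basis for the size or direction of the bias. Counting safety calls would measure contact with participants and say nothing about bias.

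**The case for a change.** The strongest case for a change is that this is the primary endpoint and it depends on asking. The side effects that section 2.2.1 reports from a 16-session trial are largely symptoms learned by questioning: insomnia, vivid colours, an odd taste and irritability. Participants may have an MMSE score as low as 14 (section 5.1), which gives an interviewer room to influence what is reported. There is no DSMB or safety monitoring committee, and oversight rests with a co-PI active in the trial (section 10.1.4). One clause would remove the doubt.

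Part of this stands. No sentence says that the list is coded, and none says that those who elicit or classify adverse events are blind. Participant blinding would not stop an unblinded caller from probing unevenly.

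What does not stand is the step from silence to unblinding. The shared label of study staff cannot show that callers know the arm, because the expressly blind rater carries the same label. Nor can the text available here settle whether the list provider also classifies events, since both names were removed. The titles that remain differ: co-investigator in section 6.3, co-PI in section 10.1.4.

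**Conclusion.** No change to the plan follows. The list sentence omits a detail that the rest of section 6.3 supplies by implication: staff are meant to work blind, with the key sealed. A team following those provisions would collect adverse events without knowing the arm, and the between-group count would be sound in this respect. Extra wording would record what the plan already intends and would leave the endpoint, the data and the analysis as they are.

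This rests on three assumptions that the documents support but do not state: the list carries codes; the codes are specific to each participant, so that opening one envelope does not reveal the others; and the co-investigator who holds the key does not question participants about adverse events. They concern the 16-week sham-controlled phase only, because treatment is known in the optional open-label phase. If the list in use did show treatment names to callers, the concern would be real, but nothing in the documents shows that.

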8 STUDY ASSESSMENTS AND PROCEDURES

8.1 ENDPOINT AND OTHER NON-SAFETY ASSESSMENTS

Cognitive and Behavioral Outcome Measures will be assessed at baseline and after 16 weeks by a study staff member who will be blind to treatment assignment. The measures are standard in the field and have well-established validity and reliability:

- The **Mini-Mental State Exam (MMSE)** (Folstein et al., 1975) is a fully structured screening instrument frequently used for Alzheimer’s disease drug studies. The scale evaluates orientation, memory, attention, concentration, naming, repetition, comprehension, and ability to create a sentence and to copy two overlapping pentagons.
- The **Alzheimer’s Disease Assessment Scale, Cognitive Subscale (ADAS-cog)** (Rosen et al., 1984) is a structured scale that evaluates memory (word recall, word recognition), reasoning (following commands), language (naming, comprehension), orientation, ideational praxis (placing letter in envelope) and constructional praxis (copying geometric designs). Ratings of spoken language, language comprehension, word finding difficulty, and ability to remember test instructions are also obtained. The test is scored in terms of errors, with higher scores reflecting poorer performance. Scores can range from 0 (best) to 70 (worse).
- The **Color Trails Test (CTT)** (D’Elia et al., 1996) is a non-verbal test of visual attention, graphomotor sequencing, and effortful executive processing abilities (i.e., sustained attention and set shifting).
- The **Neuropsychiatry Inventory (NPI)** (Cummings, 1997) is a well-validated, reliable, multi-item instrument to assess psychopathology in AD based on an interview with a study companion or qualified partner.
- The **Alzheimer’s Disease Cooperative Study, Activities of Daily Living (ADCS-ADL)** (Galasko et al., 1997) assesses the competence of patients with AD in basic and instrumental activities of daily living (ADLs). It can be completed by a caregiver in questionnaire format, or administered by a clinician/researcher as a structured interview with a caregiver.

Cerebrospinal fluid (CSF) and blood biomarkers: The Quanterix HD-1 analyzer will be used for automated multiplex quantification of proteins in biofluids, including plasma, serum and CSF. The HD-1 platform uses Single Molecule Array (SiMoA) technology, a digital form of ELISA with a 1000-fold higher sensitivity compared to other immunoassay techniques. This methodology offers high precision (coefficient of variations below 10%), efficiency (2.5 hours per 96-well plate), wide dynamic range (spanning > 4 logs) and capabilities for homebrew assay development. Ten mL of blood sample will be collected from each patient by venipuncture red-top or ethylenediaminetetraacetic acid (EDTA) tubes for serum and plasma. Ten mL of CSF will be collected by LP into polypropylene tubes according to the Alzheimer’s Disease Neuroimaging Initiative (ADNI) protocol (<http://www.adni.info.org/ADNIStudyProcedures/LumbarPunctures.aspx>). $A\beta_{1-40}$, $A\beta_{1-42}$, total tau, NfL, UCHL1, MCP-1, MCP-3, MIP-1 β , VEGF, and BDNF will be measured from blood. These analytes and p-tau will be measured from CSF.

8.2 SAFETY ASSESSMENTS

Study staff will call the subject and his/her study partner twice a month to for safety assessments.

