tPBM risks: The safety of one session of tPBM was evaluated in three large RCTs with a pooled sample of 1,410 subjects with stroke (Lampf et al., 2007; Huisa et al., 2013; Zivin et al., 2014). No significant difference in the rate of adverse effects were observed between the group receiving laser NIR (808 nm; 5W) or sham. Two open studies using 1 and 6 sessions of tPBM reported no treatment-emergent side-effects (Hacke et al., 2014; Lampf et al., 2007). A clinical trial with 16 sessions reported an increased number of mild side-effects in the active treatment group, the most frequent being insomnia, "seeing vivid colors", "an ashtray-like taste", and irritable mood (Hipskind et al., 2019). Other potential risks relate to inappropriate administration and will be mitigated by the safety procedures such as the use of protective eye wear. The risk of thermal injury from PBM delivered with the parameters used in the studies we reviewed is considered minimal and limited to the skin. In ten individuals treated for TBI with 10-15W lasers—a much higher power than what is used in tPBM—the skin temperature increased to no more than 30°C with rapid cooling after removal of the NIR light. Clinically, patients reported slight skin warming, but no discomfort (Hipskind et al., 2019). Inherent to the use of any laser device is the potential risk of retinal lesions resulting from improper use of the laser and from the shedding of the light beams straight through lens and from their convergence on the macula; this is mitigated with appropriate safety eyewear and procedures.

There have been no documented risks associated with the Vielight Neuro Gamma device. The Vielight Neuro Gamma device is a portable, wearable, low-light level therapy delivery device that administers near-infrared light to the brain transcranially and intranasally. The device can be applied by the study partner at home and does not require specialized training. The controller houses a NiMH battery and controlling electronics for the Neuro Rx Gamma device. Both the Headset and Nasal Applicator are connected to the controller with connectors that prevent them from being incorrectly inserted. A single

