8.3.4 TIME PERIOD AND FREQUENCY FOR EVENT ASSESSMENT AND FOLLOW-UP

The occurrence of an AE or SAE may come to the attention of study personnel during study visits and interviews of a study participant presenting for medical care, or during the bi-monthly check-ins. All AEs including local and systemic reactions not meeting the criteria for SAEs will be logged. Information to be collected includes event description, time of onset, clinician's assessment of severity, relationship to study product (assessed only by those with the training and authority to make a diagnosis), and time of resolution/stabilization of the event. All AEs occurring while on study must be documented appropriately regardless of relationship. All AEs will be followed to adequate resolution.

Any medical condition that is present at the time that the participant is screened will be considered as baseline and not reported as an AE. However, if the study participant's condition deteriorates at any time during the study, it will be recorded as an AE. Unexpected problems (UPs) will be recorded in the data collection system throughout the study.

Changes in the severity of an AE will be documented to allow an assessment of the duration of the event at each level of severity to be performed. AEs characterized as intermittent require documentation of onset and duration of each episode.

The PI will record all reportable events with start dates occurring any time after informed consent is obtained until 7 (for non-serious AEs) or 30 days (for SAEs) after the last day of study participation. At each study visit, and at the bi-monthly check-ins, the investigator will inquire about the occurrence of AE/SAEs since the last visit. Events will be followed for outcome information until resolution or stabilization.

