9.3.2 ANALYSIS OF THE PRIMARY ENDPOINT(S)

Safety and AEs will be assessed at each in-person study visit and during bi-monthly check-ins. We will use Kolmogorov-Smirnov test to compare the number of AEs in each group. To examine tolerability, we will determine the total number of treatment days and average treatment days per week in each group.

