says is OK with me” is fine. The demonstration of assent need not be verbal. Passive lack of objection is acceptable in an alert patient. Signs of dissent may include verbal statements as well as non-verbal cues such as shaking their head no or appearing to be agitated or distressed. These signs will be taken as refusals to assent to the study. The LAR may participate as the study partner or may designate another person (e.g., another family member, paid caregiver) to participate as the study partner on their behalf.

Because study partners will also be actively participating in the study (by providing information about the participant's memory, behaviors, and daily functioning), they will also sign a separate consent form. If the LAR is unable to participate in the consent visit in person (e.g., lives remotely), the consent forms may be mailed to them, reviewed with the research team over the phone, signed and mailed back; however, the participant must still provide assent. The study caregiver may also choose to have the consent form mailed to them, reviewed by phone, signed and mailed back. Finally, research staff will sign both forms and will indicate that an assent discussion was completed if appropriate.

The PP will also be provided with a large handout, separate from the consent, that has the PIs' names and phone number so the PP can call the PIs, separate from his/her study partner should s/he wish to do so. In addition, a study staff member will speak to the PP during the Confirmation Visit and during the "check-in" calls, which will occur once every 2 weeks following the Confirmation Visit. On these occasions, the study staff member will speak to the PP separate from the study partner, to see how the study is going for the PP and to ask if the PP still wishes to participate in the study.

There is an 'optional' open-label study phase for eligible participants who complete the placebo-controlled phase and wish to receive active PBM. At the time of initial consent subject may opt in or out of the 'optional' open-label phase by checking boxes on the ICF. We will re-confirm their decision before they start the open-label extension phase.

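### Adverse events, the primary endpoint, are sought between visits by recall about every two weeks, while the home diary is described only as a treatment log

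*Combined protocol and SAP*

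**What the plan says.** Section 3 states: "The primary endpoint will be all adverse events". Section 8.3.1 defines an adverse event broadly enough to include any symptom or experience that appears or worsens, so mild subjective complaints count.

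Between visits, section 8.2 provides: "Study staff will call the subject and his/her study partner twice a month to for safety assessments". Section 6.2.1 agrees: "A study staff will contact the patient and study partner twice a month to assess for adverse events". Section 10.1.1.2 describes check-in calls "which will occur once every 2 weeks following the Confirmation Visit". Sections 8.3.4 and 9.3.2 add in-person visits: "At each study visit, and at the bi-monthly check-ins, the investigator will inquire about the occurrence of AE/SAEs since the last visit" and "Safety and AEs will be assessed at each in-person study visit and during bi-monthly check-ins". The term bi-monthly could mean two things, but sections 6.2.1, 8.2 and 10.1.1.2 settle it as about every two weeks. The schedule in section 1.3 shows no assessment visit between baseline (week 2) and week 19. Section 6.2.1 has a skills check one week after training, and section 10.1.1.2 mentions a Confirmation Visit.

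On the diary, section 6.2.1 says: "The study partners will be asked to log the tPBM treatments throughout the 16-weeks in a home treatment diary". Nothing in the documents gives it a symptom or adverse-event field.

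On expected effects, section 2.2.1 cites a 16-session trial that "reported an increased number of mild side-effects in the active treatment group". The most frequent were insomnia, vivid colors, an ashtray-like taste and irritable mood. For an intermittent event, section 8.3.4 wants the start and length of every occurrence recorded.

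**The concern.** The endpoint that carries the trial's safety conclusion is only as complete as the method that finds the events. Here a patient with impaired memory, or a partner, is asked to look back over about two weeks and six sessions. Two of the four effects named in section 2.2.1 are private sensations, so if the patient forgets them nobody else can supply them. A symptom that came after some sessions and not others would also have to be dated episode by episode from memory.

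The trial's hypothesis is that treatment is safe. Lost events make both arms look cleaner and shrink the absolute difference between them. Events not recorded at the time cannot be recovered later. The partner already makes a written record of the treatments, and that record is not used for symptoms.

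**Working it through.** The documents state no adverse-event rate, recall fraction or power for the primary endpoint, so there is no figure to reproduce. What can be checked is the density of contacts and, by assumption, what incomplete capture would do.

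**Contacts and sessions.** Treatment lasts 16 weeks, or 112 days.
- Twice a month is one call per 365.25/24 = 15.2 days, so 112/15.2 = 7.4 calls. Every two weeks gives 16/2 = 8 calls.
- Three sessions a week (section 4.1) gives 3 × 16 = 48 sessions. Every other day (one of the options in section 6.1.2) gives 112/2 = 56.
- Sessions per call: 48/8 = 6 to 48/7.4 = 6.5, or 56/8 = 7 to 56/7.4 = 7.6.

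A diary line per session would therefore give 48 to 56 capture points in place of 7 to 8.

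**Chance of seeing an effect at all.** Let p be the true proportion of active patients affected, q the fraction of those captured, and n the number of active patients. The chance of at least one recorded case is 1 − (1 − pq)^n. With n = 8 (section 9.2) and p and q assumed:

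| p | q = 1 | q = 0.5 | q = 0.25 |
|---|---|---|---|
| 10% | 57% | 34% | 18% |
| 20% | 83% | 57% | 34% |
| 30% | 94% | 73% | 46% |

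For p = 20%: 1 − 0.8^8 = 0.83, 1 − 0.9^8 = 0.57, 1 − 0.95^8 = 0.34. The synopsis gives 14 patients, which is 7 per arm at 1:1; the same row is then 79%, 52% and 30%.

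**The planned comparison.** Section 9.3.2 compares adverse-event counts by the Kolmogorov-Smirnov test. With 8 per arm the exact two-sided 5% criterion (ignoring ties) is D ≥ 6/8 (p = 0.019; D = 5/8 gives p = 0.087). With 7 per arm it is D ≥ 6/7. Assume Poisson counts with mean 1 in sham and 4 in active, and the same capture fraction q in both arms. The recorded excess is then q × (4 − 1). Simulated power (200,000 runs per cell):

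| q | recorded excess | 8 per arm | 7 per arm |
|---|---|---|---|
| 1 | 3.00 | 67% | 45% |
| 0.75 | 2.25 | 49% | 29% |
| 0.5 | 1.50 | 28% | 14% |
| 0.25 | 0.75 | 11% | 5% |

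With rarer events (means 0.25 and 1.25, 8 per arm) the test has about 20% power at full capture, 12% at q = 0.75, 5% at q = 0.5 and under 1% at q = 0.25.

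**The case against.** Calls are not the only route. Events are also asked about at in-person visits and may surface when a patient seeks care (sections 8.3.4, 9.3.2). Section 8.3.4 requires active inquiry, and section 2.2.1 promises proactive, ongoing assessment. On the check-in calls staff also speak to the patient apart from the partner (section 10.1.1.2), although the stated purpose is to ask how the study is going and whether the patient wishes to continue. A partner can often notice insomnia and irritability. Prodromal patients are eligible, so not every participant has dementia. Call scripts and diary forms may sit in the Manual of Procedures, which section 10.1.7 mentions. For a small pilot of a device that section 6.1.1 calls low risk, contact every two weeks is defensible. All of this stands. It narrows the point but does not supply capture near the session for private symptoms, or a basis for dating each episode.

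A reader might go further and infer that device effects are selectively lost and the comparison biased in a known direction. The documents do not support that. Section 2.2.1 calls the effects mild and gives no duration, so it cannot be said that they are too brief to be recalled. The documents are silent on how the calls are structured, which does not show that they are unstructured. The calls are planned alike for both arms, and the calculation above assumes equal capture. It shows under-counting and lost sensitivity, not differential loss.

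It is also fair to say that better capture would not by itself give the planned test adequate power. Under the lower assumed rates, power is about 20% even with nothing missed.

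**Conclusion.** The concern holds as a weakness in how the primary endpoint is captured, with a cheap remedy. Between few visits, adverse events depend on recall over about two weeks and about 6 sessions (up to 7.6 if treatment is every other day), from patients with MMSE 14 to 30 and a partner. The diary is described only as a treatment log.

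The likely harm is under-counting in both arms and reduced sensitivity to a device-related excess. How much is unknown. If half of the affected patients went unrecorded, an effect present in 20% of patients would have a 57% rather than 83% chance of appearing among 8 active patients. With assumed means of 1 and 4 events, power of the planned test would fall from 67% to 28%. These figures rest on assumed rates, assumed capture fractions common to both arms, Poisson counts and 8 per arm. They illustrate sensitivity and do not predict this trial's result.

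**What to change.** Add to each treatment entry in the home diary one prompt, *any symptom since the last session?*, with date and duration, and tick boxes for the effects named in section 2.2.1. The partner asks the patient and fills it in, with identical wording in both arms. State in sections 6.2.1 and 8.2 that staff review these entries at the calls already planned. In section 9.3.2, report solicited (diary) and spontaneous events in separate tables.

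The cost is a short entry at about 48 sessions (56 if every other day), with no added visit or staff. The downside is a small burden on the partner and more minor events reported in both arms, because prompting raises reporting; the separate tables keep that visible. While these sections are open, the sponsor should also reconcile the session frequency between sections 4.1 and 6.1.2, and the total of 14 in the synopsis with 8 per arm in section 9.2, since both set how many entries and patients the safety comparison rests on.
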